An intent-to-treat, stratified log rank test will be used to test whether or not the single-fraction SRS arm is inferior to the hypofractionated (3 fractions in total) SRS arm in terms of the local control rate. To set up a formal test we will use the 1-year local control rate as the surrogate of the efficacy (assuming that the two survival curves follow exponential distributions) and allow a 10% inferior margin. From a clinical standpoint, the investigators agreed that a difference of less than 10% is not regarded as significant. On this basis, we permit a 10% inferior margin. I.e., we will test $H_0: P_1 \leq (P_2 - 10\%)$ vs $H_1: P_1 > (P_2 - 10\%)$, where P_1 and P_2 denote the 1-year local control rate for the single-fraction arm and the 3-fraction arm, respectively. To approximately assess the power of the test, we estimate that the 3-fraction arm will yield a 1-year local control rate around 85% based on interim preliminary data from a multicenter Phase III trial (Protocol 10-154), and set the type I error (that is, declare single-fraction arm noninferior while it is not) rate at 0.10. When the two arms have equal efficacy, i.e., $P_1 = P_2 = 85\%$, the power (that is, declare the single-fraction arm noninferior while it is) of this noninferiority test⁴⁰ is 80% when there are 75 patients in each arm. Besides, since deaths without local failure are likely, competing risk analysis will also be used to estimate the local control rates of the two arms over time. We plan to enroll 150 patients within 2 years. If a

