Toxicity outcomes and patterns of complications are summarized and tabulated in Section 11.0. Comparisons will be made using Wilcoxon rank sum tests and proportion tests. QOL results measured by MDASI scores and pain control results measured by BPI scores will also be summarized and compared between the two arms by Wilcoxon rank sum tests. As multiple measurements will be taken and thus multiple tests will be conducted, test p-values will be adjusted by the false discovery rate method.

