15.2 Randomization

Randomization will be centralized at MSKCC. Patients will be randomized to the single dose arm (24 Gy) or the multi-dose arm (27 Gy in 3 fractions). Ineligible lesions and other lesions not being treated on protocol will be treated according to standard of care at the physician's discretion. Immediately after consent is obtained at MSKCC and at participating sites, the RSA will register participants in the Protocol Participant Registration (PPR) system. Once the participant's eligibility is established, the registration will be finalized and the participants will

be randomized using the Clinical Research Database (CRDB). Randomization will be accomplished by the method of random permuted block, and will be stratified by institution, prior radiation history, and radioresponsiveness of the primary disease site (radioresponsive tumors include prostate, lung, breast, etc and non-responsive tumors include melanoma, renal cell, colon and sarcoma). After the treatment arm is determined by randomization, the RSA will notify the research staff and/or investigators at MSKCC and participating sites of the treatment arm and participant ID via email within 24 hours of randomization.

Data will be collected at other centers and sent to the RSA(s) at MSKCC according to Table 6. Compiled data will be submitted to the biostatisticians at MSKCC for analysis.

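### Secondary comparisons leave out the randomisation factors: adjusting MDASI, BPI and common toxicities for them as main effects would gain up to about 6 points of power if the factors are prognostic, at little cost

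*Combined protocol and SAP*

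**What the plan says.** Section 15.2 states that randomisation, by permuted blocks, "will be stratified by institution, prior radiation history, and radioresponsiveness of the primary disease site". Section 14.0 lists the same three factors. For the primary endpoint, Section 14.0 follows the design: "An intent-to-treat, stratified log rank test will be used".

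For toxicity and complications the last paragraph of Section 14.0 says "Comparisons will be made using Wilcoxon rank sum tests and proportion tests". MDASI and BPI scores are to be "compared between the two arms by Wilcoxon rank sum tests", and "test p-values will be adjusted by the false discovery rate method". That paragraph names no strata and no covariates, and no other section supplies an adjusted secondary analysis. No test level, false discovery rate level, power or effect size is given for any secondary endpoint.

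**The concern.** Stratified allocation removes most of the chance imbalance in the stratifying factors. An unstratified test still counts the variation due to those factors as noise, so its standard error is too large to the extent that they predict the outcome. The true size then falls below nominal and some power is lost. The plan deals with this for local control but not for the endpoints named as secondary objectives in Section 2.0.

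The stake is sensitivity. Section 14.0 says that, if local control proves comparable, cost and toxicity are to guide the choice of schedule. In a safety comparison a conservative test makes a real difference easier to miss. Information is already limited: 75 patients per arm, optional questionnaires (Section 10.0, Table 1), expected deaths, and a multiplicity adjustment on top.

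**Working it through.** **The plan's own figure.** The only stated power is 80% for the primary test. The margin hazard ratio is ln(0.75)/ln(0.85) = 1.770. With 2 years of accrual, 2 further years of follow-up and no deaths, expected events are 150 × 0.383 = 57.5. Power at one-sided 0.10 is Φ(√(57.5/4) × ln 1.770 − 1.282) = Φ(0.88), about 81%. The figure reproduces if deaths are ignored. There is no corresponding figure to reproduce for the secondary tests.

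**Inputs.** From the documents: 150 patients, 1:1 allocation, permuted blocks, and 4 centres × 2 × 2 = 16 cells, or 150/16 ≈ 9 patients per cell. Assumed: blocks of 4, equal centres, prior radiation in 50%, radioresistant histology in 70%, two-sided 5% tests, and R², the share of outcome variance explained by the three factors, from 0 to 0.20.

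**Approximate size of an unstratified test.** Size = 2 × [1 − Φ(1.96/√(1 − R²))]:
- R² = 0.05: 4.4%
- R² = 0.10: 3.9%
- R² = 0.20: 2.8%

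**Simulation for scores, all 150 patients, true shift 0.46 SD for power.** Rank regression has the three factors as main effects.

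| R² | Wilcoxon size | Rank regression size | Wilcoxon power | Rank regression power | Gain |
|---|---|---|---|---|---|
| 0 | 4.9% | 4.8% | 77.2% | 77.3% | 0.1 |
| 0.05 | 4.3% | 5.0% | 76.8% | 78.3% | 1.5 |
| 0.10 | 4.2% | 5.1% | 77.8% | 80.5% | 2.7 |
| 0.20 | 3.4% | 4.7% | 80.1% | 85.9% | 5.8 |

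Further independent runs gave Wilcoxon sizes of 5.0–5.3% at R² = 0, 3.9–4.1% at 0.10 and 2.8–3.1% at 0.20. One of them also repeated the power comparison: 77.4 to 77.3, 79.4 to 82.4 and 78.5 to 84.6 at R² of 0, 0.10 and 0.20. Monte Carlo error is about 0.2–0.3 points for size and 0.5–0.7 for power.

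**Half the questionnaires missing (assumed; n = 75, shift 0.65 SD).** Power of Wilcoxon against main-effects rank regression is 76.9 vs 75.8 at R² = 0, 76.0 vs 76.9 at 0.05, 76.6 vs 79.3 at 0.10 and 77.3 vs 83.5 at 0.20. The loss at R² = 0 was 1.0 point here and 1.6 in another run.

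**A rank test stratified over all 16 cells (van Elteren).** With 150 patients its power against Wilcoxon is 73.5 vs 76.6 at R² = 0, 79.2 vs 78.3 at 0.10 and 83.0 vs 79.4 at 0.20. With n = 75, under 5 patients per cell, it is 65.5 vs 76.4, 69.5 vs 76.2 and 76.9 vs 77.8. The loss at R² = 0 is therefore about 3 points, or about 11 with half the questionnaires missing.

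**Toxicity at 5–10%.** With factor odds ratios of 1 to 3 (assumed), size is 4.4–5.1% for the proportion test and 4.4–5.2% for Cochran-Mantel-Haenszel. Stratifying changes power by −1.0 to +2.6 points.

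**Common toxicity.** The documents give no fracture rate, so 25% and 40% are assumed. With odds ratios of 3 for prior radiation and histology and a comparable centre spread, the proportion test's size is 3.7% and 4.0%, against 4.8% and 5.2% with main-effects adjustment. Power rises from 69.1% to 72.8% and from 67.5% to 72.6%. At odds ratios of 2 the gain is about 2 points. With non-prognostic factors adjustment costs at most 0.6 points, within the Monte Carlo error of about 0.8.

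**The case against.** An unadjusted rank or proportion test in a randomised trial is valid. Any error is towards fewer false positives, and the size of the effect rests on an R² that the documents do not give. With weak factors (R² up to 0.05) the true size is 4.3–5.3%, close to nominal. All of this stands, and it makes the point one of efficiency.

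Three stronger readings are tempting and are not supported.

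- A reader might infer that every secondary test is conservative. That holds only as far as the factors are prognostic, and no section says how strongly they predict symptom scores or toxicity, or that grading differs by centre.
- A reader might infer that toxicity is affected as much as the scores. Section 14.0 expects grade 4 toxicity below 10%, Section 11.1 puts more significant toxicity below 1%, and Section 3.7 cites 6.8% for grade 3 or worse oesophageal toxicity. With odds ratios of 2 for all three factors (assumed), R² is only 0.3%, 1.7% and 2.4% at event rates of 1%, 7% and 10%, giving sizes of 4.97%, 4.8% and 4.7%. The exception is common toxicity: Section 17.2 describes vertebral fracture as common, and Section 14.0 names it as the toxicity that may be higher after single-fraction treatment.
- A reader might infer that any stratified method recovers precision for nothing, for example 150/(1 − 0.10) = 167 effective patients. That ratio is a linear-model result and starts from 150 complete questionnaires. It does not carry over directly to logistic or proportional-odds models, where adjustment also changes the odds ratio being estimated. The 16-cell rank test can lose power outright.

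**Conclusion.** The point holds in limited form and is minor. For R² from 0 to 0.20, the MDASI and BPI tests have a true size of about 5% falling to about 3% and give up 0 to about 6 points of power compared with main-effects adjustment. Common toxicities lose less: about 2 points at factor odds ratios of 2, and about 4 to 5 at odds ratios of 3. At event rates of about 10% or below the effect is negligible.

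The plan does not bias the comparisons or inflate false positives, and the primary analysis is untouched. The sizes rest on the assumed R², event rates, block size and two-sided 5% level. The direction rests only on the factors being prognostic to some degree.

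**What to change.** Reconcile the histology factor first. Section 14.0 classes only breast and prostate as radiosensitive and the remaining solid tumours as radioresistant, whereas Section 15.2 also lists lung as radioresponsive. Until one definition is fixed, an analysis by histology as randomised is ambiguous.

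Then add to the last paragraph of Section 14.0:

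- MDASI and BPI comparisons, and comparisons of common toxicities including vertebral fracture, adjust for centre, prior radiation and histology as randomised, entered as main effects. Rank-based or proportional-odds regression would serve for the scores and logistic regression for toxicity. State the effect measure that is reported.
- The unadjusted Wilcoxon or proportion test is kept as a sensitivity analysis.
- For rare toxicities, keep the simple test or stratify on prior radiation × histology only.
- A rank test stratified over all 16 cells is not used.

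The cost is SAP wording, since the factors are already recorded at randomisation. The statistical downside is about 1 to 2 points of power if the factors turn out not to be prognostic and many questionnaires are missing.

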3.0 BACKGROUND AND RATIONALE

3.1 Metastatic spine tumors

The incidence of metastatic spine tumors is nearly 20% and has been increasing due to improvements in neo-adjuvant strategies. These allow for longer patient survival and thus increased incidence of progression to metastatic disease¹. The median survival for patients undergoing surgery for spinal metastatic tumors ranges from 7.0 – 16.5 months²⁻⁶. More specifically, the median survival varies depending on the histological type of primary cancer^{2,4}. However, with the development of superior systemic therapies which extend survival, these numbers are becoming outdated.

Diagnosis of spinal metastasis is made reliably based on clinical, radiographic and histologic grounds. Metastases to the skeletal system are the third most often involved system after the lungs and liver. Of this, nearly half are metastases of the spine. The majority of spinal metastases involve disease of the vertebral body with or without epidural compression. It is estimated that 5-10% of patients with spinal metastases will develop symptomatic spinal cord compression requiring surgical intervention⁷. The NOMS paradigm provides a widely-accepted guide to relevant considerations (Neurologic, Oncologic, Mechanical and Systemic) when determining the optimal combination of systemic, radiation and surgical therapies for individual patients with spinal metastases⁸. Yet despite advances in surgical and radiologic treatments, local recurrence of spinal metastasis remains a challenging problem and can lead to progression of spinal column instability, nerve/spinal cord compression and may require repeat surgery^{9,10}. Further study on improving the local recurrence of spinal metastases is warranted and has great clinical implications for the evaluation and counseling of patients.

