6.0 CRITERIA FOR SUBJECT ELIGIBILITY

6.1 Subject Inclusion Criteria

- 1) Histologically diagnosed metastatic cancer (Diagnosis made or confirmed at MSKCC for MSKCC participants. Institutional pathologic determination accepted from participating multicenter sites.)
- 2) Age ≥ 18 years
- 3) Life expectancy ≥ 3 months
- 4) ECOG ≤ 3
- 5) Spinal surgery carried out with the goal of spinal cord decompression and spinal stabilization within 8 weeks
- 6) Post-operative CT myelogram or MRI perfusion with evidence of separation of tumor and the spinal cord

It should be noted that patients with multiple lesions will be eligible as long as there are no overlapping fields of radiation, including at various time frames.

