patient has multiple eligible lesions, all of them will be treated within the randomized arm and each eligible lesion (non-contiguous lesions treated with a separate radiation contour) will be treated as a separate study unit. After the enrollment of the final patient, a 2-year follow up is planned. Three interim analyses are planned and will be conducted at the time of the DSMB annual review of the study. The O'Brien-Flemming boundary will be applied for assessing statistical significance. Specifically, the rejection regions in terms of the corresponding Z-scores are $Z > 3.09$, $Z > 2.06$, $Z > 1.63$ and $Z > 1.39$ for the three interim looks and the final look, respectively. We expect that very few patients will have multiple lesions and thus we do not plan to examine the correlation among multiple lesions from the same patients. Instead, the analysis of the primary endpoint will be conducted at lesion level as mentioned above. Data will be collected from all four centers and analyzed at MSKCC.

In consideration of the fact that a large cohort will be recruited, this study will be continuously monitored to protect patients from excess toxicity. For each arm, we anticipate that the true rate of any grade 4 toxicity within 24 months post SRS is less than 10%. All grade 4 toxicities or greater observed will be reviewed by the study chair. Moreover, using a stopping rule based on sequential probability ratio test (SPRT), each arm of the study is monitored for any grade 4 or above toxicities that are judged to be associated with the radiation treatment. This stopping rule specifies that for each arm, the study will be halted if any of the following conditions occur: >4 /first 15; >6 /first 35; >9 /first 55; or if more than 12 unacceptable toxicities are observed within 24 months post SRS when the last (75th) patient has completed the trial. When the true toxicity rate is 10%, this stopping rule has a probability of 0.1 to stop the trial. When the true toxicity rate is 20%, this stopping rule has a probability of 0.8 to stop the trial. For this stopping rule we will use each patient as a study unit.

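### Late radiation toxicity is compared by crude proportions, with no rule for patients lost to follow-up and no means of separating toxicity hazard from survival

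*Combined protocol and SAP*

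**What the plan says.** Section 14.0 compares toxicity outcomes in one sentence: "Comparisons will be made using Wilcoxon rank sum tests and proportion tests". Scores for quality of life and pain are also compared by rank sum tests, and p-values are adjusted by false discovery rate. No denominator, follow-up window or handling of death or loss is given for toxicity.

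For the primary endpoint the same section reasons differently: "since deaths without local failure are likely, competing risk analysis will also be used to estimate the local control rates".

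Section 11.1 splits toxicity at 90 days into acute and late, and Section 11.2 monitors adverse events for 24 months after SRS or until death. Section 13.0 lists loss to follow-up among the reasons for leaving the study.

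On survival, Section 3.1 states: "The median survival for patients undergoing surgery for spinal metastatic tumors ranges from 7.0 – 16.5 months". It adds: "However, with the development of superior systemic therapies which extend survival, these numbers are becoming outdated". Section 6.1 requires "Life expectancy ≥ 3 months".

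The per-arm stopping rule in Section 14.0 starts from the statement that "we anticipate that the true rate of any grade 4 toxicity within 24 months post SRS is less than 10"%. It halts the study at more than 4 of the first 15 patients, 6 of 35, 9 of 55 or 12 of 75, and gives stopping probabilities of 0.1 and 0.8 at true rates of 10% and 20%. It does not say whether those rates allow for death, or how long a patient must be followed to count in the first 15, 35 or 55.

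**The concern.** Late toxicity can be seen only in patients who are alive and under observation. If many die before 24 months and some are lost, a simple proportion reflects three things at once: how often toxicity occurs, how long patients live, and how completely they are followed. The plan recognises this for local control and does not carry it over to toxicity.

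This matters because Section 14.0 justifies the non-inferiority design by saying that comparable control would let physicians choose on factors such as cost and toxicity risk. Vertebral fracture is the named worry for the single-fraction arm. The toxicity comparison is formally secondary, but it is one of the results on which that choice would rest.

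**Working it through.** **Step 1. Reproduce the stopping-rule figures.** Inputs: the four boundaries and 75 patients per arm (Section 14.0). An exact binomial recursion over looks at 15, 35, 55 and 75 patients gives, as the chance of first crossing at each look:
- rate 10%: 0.0127 + 0.0468 + 0.0185 + 0.0097 = 0.088 (stated 0.1)
- rate 20%: 0.1642 + 0.4106 + 0.1584 + 0.0886 = 0.822 (stated 0.8)

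Both agree at the one decimal given. They are binomial probabilities in which each patient has the full stated chance of an observed event, so they hold when the rate is the share of treated patients who have one.

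**Step 2. Deaths before 24 months.** Input: median survival M of 7.0 to 16.5 months (Section 3.1); exponential survival is assumed. Share dead = 1 − 0.5^(24/M): 91% at M = 7, 75% at 12, 64% at 16.5. At an assumed median of 24 months it is still 50%.

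**Step 3. What the crude proportion estimates.** Let h be the toxicity hazard, l = ln 2/M the death hazard and c the loss hazard, all per month and independent. The expected crude proportion is

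P = h/(h + l + c) × (1 − exp(−24(h + l + c))).

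With c = 0 this is the cumulative incidence with death as a competing event. Take a 20% risk in the absence of death, so h = −ln(0.8)/24 = 0.00930, and M = 12, so l = 0.05776. Then P = 0.1386 × 0.800 = 11.09%. A simulation of one million patients gave a crude proportion of 11.06%. With complete follow-up, death does not bias the proportion as an estimate of the share affected.

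**Step 4. Loss to follow-up.** The documents give no loss rate, so 10% and 20% a year are assumed, with c = −ln(1 − annual loss)/12. Lost patients stay in the denominator without an event. For M = 12 and h as above:
- 10% loss: c = 0.00878, P = 0.1226 × 0.838 = 10.27%, ratio to no loss 0.926
- 20% loss: c = 0.01860, P = 0.1085 × 0.872 = 9.47%, ratio 0.853

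| Risk without death | Median survival (months) | No loss | 10%/year | 20%/year |
|---|---|---|---|---|
| 10% | 7 | 3.89% | 3.65% | 3.41% |
| 10% | 12 | 5.47% | 5.06% | 4.65% |
| 10% | 16.5 | 6.35% | 5.84% | 5.33% |
| 20% | 7 | 7.95% | 7.46% | 6.98% |
| 20% | 12 | 11.09% | 10.27% | 9.47% |
| 20% | 16.5 | 12.83% | 11.82% | 10.82% |

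The shortfall against the true cumulative incidence runs from about 6% to 16% in relative terms.

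**Step 5. Equal toxicity hazard, unequal survival.** Same h, c = 0, assumed medians of 9 and 14 months:
- M = 9: l = 0.07702, P = 0.1077 × 0.8740 = 9.4%
- M = 14: l = 0.04951, P = 0.1581 × 0.7562 = 12.0%

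The gap comes entirely from survival. With 75 per arm, a two-sided 5% proportion test would reject with probability 0.057 at medians of 10 and 14 months (10.0% versus 12.0%), and 0.16 at the extremes of 7 and 16.5 months (7.9% versus 12.8%).

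**The case against.** The strongest reply is that the proportion is right for what it measures. With follow-up to death or 24 months it equals the competing-risk cumulative incidence, so a 24-month cumulative incidence would return the same number. This stands.

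It also answers two stronger inferences a reader might draw: that late toxicity is heavily understated, and that the stopping rule loses most of its chance of halting. Both compare the observed share with a risk in a world without death, which the documents never claim to estimate. Their size also depends on event timing, which is not given. For a 20% no-death risk and medians of 7 to 16.5 months, the observed share is 7.9-12.8% with constant hazard, but 17.4-18.8% if every event falls in the first 3 months. The stopping rule counts observed toxicities per patient. If 20% is the share of patients with an event, the probability remains 0.82.

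The survival inputs are also soft. The protocol calls them outdated, they describe patients from surgery, and eligibility requires a life expectancy of at least 3 months. This stands as a caveat.

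A 9-versus-14-month split by chance is unlikely. With about 63 and 52 deaths by 24 months, the log hazard ratio of 0.44 has a standard error near 0.19 (z about 2.4, roughly 2% two-sided), and it shifts toxicity by only about 7 versus 9 patients. With similar survival in the two arms, the randomised proportion test is valid.

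Finally, Section 14.0 does not state its denominator, so counting lost patients as toxicity-free is what a plain proportion of treated patients does rather than a rule the plan writes down. That silence is itself part of the point.

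**Conclusion.** The concern holds in limited form. The plan states no toxicity estimand and no handling of losses, and its method cannot attribute a between-arm difference in late toxicity to toxicity rather than survival. The loss bias is about 6-16% relative, assuming 10-20% annual loss, constant independent hazards and exponential survival at the quoted medians. The survival effect is small for modest imbalances (9.4% versus 12.0% in the example) and grows only if survival differs markedly by arm.

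The documents do not show the crude proportion to be wrong as a share of patients with toxicity when follow-up is complete, and they do not show the stopping probabilities to be wrong; those reproduce. What is missing there is a statement of what the 10% and 20% rates mean. The change is worth making because it costs little and the toxicity comparison is meant to inform the choice of regimen.

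**What to change.** In Section 14.0, for late toxicity (Grade 3 or above, Grade 4 or above, and vertebral fracture):
- Replace the proportion test with an analysis of time to first event.
- Report 12- and 24-month cumulative incidence by arm, with death as a competing event and losses censored at last assessment.
- Compare arms by cause-specific hazard ratio. Gray's test may be added, with a note that it compares cumulative incidence and so also responds to survival differences.

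Keep proportion tests for acute (90-day) toxicity.

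For the stopping rule, state that the 10% and 20% rates are shares of treated patients with an event, with death competing, and show follow-up time beside the counts at each look. The boundaries need no change on this account.

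The cost is SAP wording and routine programming. Section 11.2, item 2, already collects adverse-event start dates. Because that section defines reportable toxicity as Grade 3 and above, any lower-grade fracture included should be dated from the imaging that first shows it.
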